Study Protocol

Protocol ID: 2025ZSLYEC-747

Title: Exploring the Clinical Value of an AI-Assisted Patient Self-Assessment App for Bowel

Preparation: A Multicenter Study

Document date: 9,1, 2025

Background and aim

Colonoscopy is a key tool for screening, diagnosing and treating colorectal cancer. Early detection and removal of polyps can substantially reduce both the clinical burden and the economic cost of advanced-stage disease. Adenoma detection rate (ADR)—the proportion of colonoscopies in which at least one adenoma is found—is the principal quality indicator; every 1 % drop in ADR increases subsequent cancer risk by 3 %. Adequate bowel preparation improves ADR, cuts the miss rate for polyps and cancers, and lowers post-colonoscopy cancer incidence, whereas poor preparation decreases polyp/ tumour detection, prolongs insertion time, increases endoscopist fatigue and may raise procedure-related complications. Yet 20–25 % of examinations are still performed under sub-optimal conditions.

The quality of cleansing depends largely on patient compliance with the purgative regimen, so intensive education is essential. Telephone calls, text messages, short videos and mini-programs have all been shown to improve compliance and preparation quality. However, early identification of individuals who are likely to prep poorly—and the opportunity to rescue them—remains an unmet need. The character of the last stool after laxative intake correlates closely with overall preparation quality; staff often ask patients to describe this stool to decide whether to proceed or delay the examination, but this is reactive rather than proactive. Allowing patients to self-assess and, if necessary, present early (out-patients) or alert staff (in-patients) for rescue could convert sub-optimal into adequate preparation.

Artificial intelligence is now widely used in gastrointestinal endoscopy. In our pilot work we developed a smartphone app that uses AI to grade stool photographs. In an internal validation set the algorithm achieved 100 % sensitivity (95 % CI 34.2–100 %) and 94.1 % specificity (90.1–96.5 %) for binary classification of adequacy. We then conducted a single-centre RCT; 461 patients (229 control, 232 app) were analysed. App users had significantly higher adequate-preparation rates (97 % vs 90 %, $P = 0.002$) and excellent-preparation rates (86.2 % vs 59.8 %, $P < 0.001$), and higher mean Boston Bowel Preparation Scale (BBPS) scores (8.2 ± 0.8 vs 7.8 ± 1.2 , $P < 0.001$) as well as segment-specific BBPS sub-scores. Cecal intubation rate, polyp-detection rate (PDR) and ADR did not differ between groups. These findings suggest the app improves preparation quality, but the single-centre design limits generalisability. We now propose a multicentre study to confirm the clinical value of this AI-assisted self-assessment tool.

Methods

Study design: a multicenter, randomized controlled clinical trial.

Location: The Sixth Affiliated Hospital, Sun Yat-sen University; Tianjin Haihe Hospital

Guangdong Second Provincial General Hospital

Dongguan Humen Hospital of Traditional Chinese Medicine

Cangzhou Central Hospital

The inclusion criteria:

- (1) Age ≥ 18 years
- (2) Undergoing colonoscopy at a participating site
- (3) Able to defecate in a toilet (or in a setting where stool characteristics can be observed) after taking the bowel-prep solution
- (4) Proficient in using a smartphone
- (5) Willing to participate voluntarily

The exclusion criteria:

- ① American Society of Anesthesiologists (ASA) class III or IV;
- ② Gastric-outlet or intestinal obstruction;
- ③ Active gastrointestinal bleeding;
- ④ Enterostomy (colostomy/ileostomy);
- ⑤ Status post total colectomy.

Intervention

After taking the bowel-prep solution, patients in the app group are instructed to photograph their final stool in the toilet and upload the image through our smartphone app. The AI algorithm immediately scores the prep quality. If the image is rated “poor” or “inadequate,” the app displays an alert advising the patient to come to the hospital early or contact clinical staff; clinical staffs then review the photo and decide whether a rescue preparation is needed. The standard rescue was an additional packet of polyethylene glycol. If the image is rated “adequate,” the patient is told the prep is acceptable and should proceed to the appointment, where clinical staffs will use the uploaded photo to confirm eligibility for colonoscopy.

The control group followed the conventional procedure: before the examination, clinical staffs asked questions and relied on the patient’s verbal description of their stool to judge the adequacy

of bowel preparation. If the prep was deemed inadequate, the standard rescue was an additional packet of polyethylene glycol.

Outcome parameters

The primary outcome parameter is the comparison of the bowel preparation quality between the app group and the control group (the rate of adequate and excellent bowel preparation).

The secondary outcome parameters are:

cecal intubation rate

cecal intubation time

withdrawal time (excluding polypectomy and biopsy)

polyp-detection rate (PDR)

adenoma-detection rate (ADR)

advanced-adenoma-detection rate (aADR)

use of rescue preparation

rate of rescheduled examinations due to inadequate preparation

clinical staffs' assessment time

user satisfaction score,

and post-procedural adverse events.

The results will be analyzed in full analysis set, per-protocol set and safety set.

Sample Size

Assuming that 16 % of patients have inadequate bowel preparation with the traditional regimen, and the app is expected to convert 25 % of these failures (i.e., 4 % of the total cohort) to adequate preparation, a sample size of 235 participants is required for $\alpha = 0.05$ and power = 0.80.

Allowing for a 10 % dropout rate, we plan to enroll 262 subjects per arm, for a total of 524 participants.

Randomization

Stratified randomization by center. Random numbers generated in Excel by an independent statistician; sequentially numbered, sealed, opaque envelopes prepared and held by the third party. The envelopes constitute the allocation sequence; random numbers remain concealed from patients and endoscopists until the envelope is opened immediately before allocation.

Blinding

Patients cannot be blinded; operators, outcomes assessors, and pathologists will remain blinded.

Statistical analysis

All analyses were performed with SPSS version 26. Baseline characteristics were examined to assess balance across concentration groups. Normally distributed continuous variables are presented as mean \pm SD and compared between groups using independent-samples t-tests; non-normally distributed continuous variables are expressed as median (interquartile range) and compared with the Wilcoxon rank-sum test. Categorical rates were compared using the χ^2 test. A two-sided $P < 0.05$ was considered statistically significant.

References

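### The primary outcome names two rates, adequate and excellent preparation, without saying which decides success; if either suffices at unadjusted P<0.05, the two-sided error is about 9%

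*Protocol*

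**What the plan says.** In the protocol, Outcome parameters gives one primary outcome, preparation quality compared between the arms, and specifies it in brackets as "the rate of adequate and excellent bowel preparation". No success rule follows.

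Statistical analysis applies to all rates alike: "Categorical rates were compared using the χ^2 test", and "A two-sided $P < 0.05$ was considered statistically significant". It states no order of testing and no adjustment.

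Two other places bear on which rate leads:

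- Sample Size uses adequacy only. It begins "Assuming that 16 % of patients have inadequate bowel preparation with the traditional regimen" and expects the app to "convert 25 % of these failures (i.e., 4 % of the total cohort) to adequate preparation". From this it concludes that "a sample size of 235 participants is required for" a 0.05 alpha and 0.80 power. Excellent preparation does not appear.
- Background and aim argues that self-assessment and rescue "could convert sub-optimal into adequate preparation". The same section reports the single-centre pilot trial as two separate results, "adequate-preparation rates (97 % vs 90 %, $P = 0.002$) and excellent-preparation rates (86.2 % vs 59.8" %, the second with its own P value of <0.001.

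**The concern.** One phrase holds two rates, and the pilot tested those same two rates separately. Followed as written, the protocol therefore allows two primary tests, each at the full 0.05. What counts as a positive trial is left open and could be settled after the results are known.

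This matters here because the two rates have very different prospects. In the pilot the difference was 97 − 90 = 7 percentage points for adequate and 86.2 − 59.8 = 26.4 points for excellent. A trial that misses on adequate and succeeds on excellent is a realistic outcome, and the present text would let it be reported as either positive or negative.

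An SAP, which is not at hand, may set a testing order or an alpha split. Which variable is the primary endpoint belongs in the protocol.

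**Working it through.** The plan states no family-wise error, so there is no figure of its own to reproduce on this point. The check works out the error under each reading of the primary outcome.

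**Inputs**

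- Patients per arm: 235 (Sample Size). It is read as per arm because 235/0.9 = 261.1, which rounds up to the stated 262 per arm.
- Each test: two-sided 0.05, critical value 1.96 (Statistical analysis).
- Adequate rate pA with no true difference: 84% (planning value, 100 − 16) or 90% (pilot control).
- Excellent rate pE with no true difference: 59.8% (pilot control), varied from 50% to 70%.
- Assumption: every excellent preparation is also adequate. The protocol does not define the two categories, so nesting is not confirmed by the text.

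**Correlation.** For nested indicators the covariance is pE(1 − pA), so

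ρ = √[ pE(1 − pA) / ( pA(1 − pE) ) ].

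- 84%/59.8%: √[(0.598 × 0.16)/(0.84 × 0.402)] = √0.2833 = 0.532.
- 90%/59.8%: √[(0.598 × 0.10)/(0.90 × 0.402)] = √0.1653 = 0.407.

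**Error.** With (Z1, Z2) bivariate normal with correlation ρ:

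- either significant = 1 − P(|Z1| ≤ 1.96 and |Z2| ≤ 1.96);
- at least one favouring the app = 1 − P(Z1 ≤ 1.96 and Z2 ≤ 1.96);
- both significant = 0.05 + 0.05 − P(either).

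| Adequate / excellent | ρ | Either, two-sided | At least one favouring the app | Both, two-sided |
|---|---|---|---|---|
| 84% / 59.8% | 0.532 | 8.98% | 4.49% | 1.02% |
| 90% / 59.8% | 0.407 | 9.31% | 4.66% | 0.69% |
| Grid 84–90% / 50–70% | 0.333–0.667 | 8.49–9.46% | 4.25–4.73% | 0.54–1.51% |
| 84% / 80% | 0.873 | 7.28% | 3.64% | 2.72% |

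For reference, two independent tests would give 1 − 0.95² = 9.75% two-sided, and a single test gives 5% two-sided and 2.5% in the app's favour. The last row shows that the grid is not a bound: the inflation shrinks when nearly all adequate preparations are also excellent.

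A multinomial simulation (235 per arm, 400,000 trials, uncorrected chi-squared) gave two-sided errors of 9.15%, 9.51% and 7.28% at 84%/59.8%, 90%/59.8% and 84%/80%, in line with the table.

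With each rate tested at two-sided 0.025, the error for either on the same grid is 4.37–4.82%.

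**Power of the adequate test with 235 per arm**, from z = (d − 1.96·SE₀)/SE₁, where SE₀ is pooled and SE₁ unpooled:

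- Planning rates, 84% vs 88%: SE₀ = √(2 × 0.86 × 0.14/235) = 0.03201 and SE₁ = √((0.1344 + 0.1056)/235) = 0.03196. So z = (0.04 − 0.06274)/0.03196 = −0.71, power about 24%.
- Pilot rates, 90% vs 97%: SE₀ = √(2 × 0.935 × 0.065/235) = 0.02274 and SE₁ = √((0.09 + 0.0291)/235) = 0.02251. So z = (0.07 − 0.04458)/0.02251 = 1.13, power about 87% (89% by exact enumeration).

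For excellent at the pilot rates (59.8% vs 86.2%), power exceeds 99% even at 0.025.

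**The case against.** The strongest reply is that nothing in the protocol says either rate alone suffices. The sentence speaks of one parameter, one comparison and a rate in the singular, and joins the two terms by a conjunction, not as alternatives. Several readings keep the error at 5% or below: adequate alone; one combined adequate-or-better rate; both required; or a single 2×3 chi-squared test across inadequate, adequate and excellent. That last test, simulated with 235 per arm and 300,000 trials, gives 5.0% at 84%/59.8% and 4.9% at 90%/59.8%. The sample size, with its single alpha and its use of adequacy alone, also points to one endpoint. The pilot's separate P values describe results and do not define success, and multiplicity control may sit in an SAP.

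Much of this is fair. The 9% belongs to one reading only, and about half of it is false results against the app. The nesting behind it is assumed. The sample size does indicate that adequate leads.

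What remains is that several readings with different error rates all fit the sentence, and nothing in the protocol chooses among them. A hint in the sample-size paragraph does not designate an endpoint when the primary-outcome sentence gives both rates equal standing. An SAP can order or weight the tests, but identifying the endpoint is the protocol's task.

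**Conclusion.** The concern holds. The primary outcome does not say which rate, or what combination of the two, decides success.

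Under the either-suffices reading the two-sided error is about 9% (8.5–9.5% over the plausible grid, 7.3% if excellent is as high as 80% with adequate at 84%). A false result in the app's favour then has a probability of about 4.2–4.7%, or 3.6% in that extreme case, against 2.5%. Under the other readings the error does not exceed about 5%. These figures assume 235 per arm, no true difference in either rate, and excellent nested within adequate.

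Apart from the error rate, the text permits a positive claim resting on a rate for which the trial was not sized.

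**What to change.** In Outcome parameters, name the rate of adequate preparation as the single primary endpoint, tested at two-sided 0.05. It is the only rate used in the sample size. Make the excellent rate the first key secondary endpoint, tested at 0.05 only if adequate is significant. If the sponsor prefers two primary rates with either sufficient, test each at two-sided 0.025. The choice should be fixed before any comparison of the arms.

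The change is one or two sentences and needs no extra patients. It has a price:

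- Excellent alone could no longer carry a positive primary claim. With 235 per arm, adequate would reach significance with about 87–89% power at the pilot rates but only about 24% at the planning rates, so at the planning rates excellent would go formally untested in about 76% of trials (100 − 24).
- With the 0.025 split, power for adequate is about 80–83% at the pilot rates and 16% at the planning rates, while excellent keeps over 99% at the pilot rates.

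The low power at the planning rates comes from the stated sample size, not from this change, and is a separate issue.

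### Could different pre-colonoscopy checks in the two arms, with rescheduling counted only as a secondary outcome, distort the primary comparison?

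*Protocol*

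**What the plan says.** Under Methods, Outcome parameters, the primary outcome compares preparation quality between arms, measured as "the rate of adequate and excellent bowel preparation". No denominator is given. The secondary list includes the "rate of rescheduled examinations due to inadequate preparation". The same section closes with "The results will be analyzed in full analysis set, per-protocol set and safety set". The sets are not defined and none is called primary.

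Under Intervention, the check before the examination differs by arm. In the app arm, "clinical staffs will use the uploaded photo to confirm eligibility for colonoscopy". In the control arm, staff "relied on the patient’s verbal description of their stool to judge the adequacy". The response to preparation judged inadequate is the same kind of rescue in both arms. Rescheduling appears only as an outcome.

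The Background says of ordinary practice that "staff often ask patients to describe this stool to decide whether to proceed or delay the examination", so postponement is a known possibility. The Blinding section covers operators, outcome assessors and pathologists. It does not cover the staff who make this check.

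**The concern.** Cleansing is presumably scored during colonoscopy. A patient turned away for poor preparation would then have no score from the index visit, or only one obtained after a second preparation. Such patients are the likeliest preparation failures. The randomised intervention includes the check that decides who is turned away, and the staff who apply it know the arm.

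If the primary rate were computed only in patients who were examined, it would depend on an event after randomisation that the intervention itself changes. A stricter photo check could then raise the app arm's adequate rate without one patient being better prepared. Blinded scoring would not help, because the selection happens before anyone is scored. The planned effect is only 4 points, so a modest difference in rescheduling could imitate it.

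**Working it through.** **Inputs from the protocol (Sample Size).** "Assuming that 16 % of patients have inadequate bowel preparation with the traditional regimen"; the app is expected to convert 25% of these; 235 patients per arm before dropout and 262 after. The planned effect reproduces: 0.25 × 16% = 4 points. So does the dropout step: 235 / 0.90 = 261.1, rounded up to 262. (The 235 itself does not follow from 16% against 12%. That is a separate matter, and 235 serves here only as the number analysed.)

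**Input not in the protocol.** The share *f* of inadequately prepared patients who are rescheduled. It is assumed to lie between 0 and 50% in each arm.

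**Formula.** Suppose 16% are truly inadequate in both arms, so the app has no benefit, and rescheduled patients are left out. Then

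adequate among those examined = 0.84 / (1 − 0.16 *f*)

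- *f* = 0: 0.84 / 1 = 84.0%
- *f* = 0.10: 0.84 / 0.984 = 85.4%
- *f* = 0.25: 0.84 / 0.96 = 87.5%
- *f* = 0.35: 0.84 / 0.944 = 89.0%
- *f* = 0.50: 0.84 / 0.92 = 91.3%

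The chance of a significant result comes from a two-sided 5% normal test of two proportions, with 235 × (1 − 0.16 *f*) patients left in each arm. For *f* = 0 in control and 0.25 in app, 235 and 225.6 patients remain. The pooled standard error is 0.0326 and the unpooled 0.0325. (1.96 × 0.0326 − 0.035) / 0.0325 = 0.89, which gives 19%.

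| *f* control | *f* app | Adequate, control | Adequate, app | App minus control | Chance the app wins | Chance control wins |
|---|---|---|---|---|---|---|
| 0 | 0.10 | 84.0% | 85.4% | +1.4 | 6% | 1% |
| 0 | 0.25 | 84.0% | 87.5% | +3.5 | 19% | 0.1% |
| 0.10 | 0.35 | 85.4% | 89.0% | +3.6 | 21% | 0.1% |
| 0 | 0.50 | 84.0% | 91.3% | +7.3 | 65% | under 0.1% |
| 0.25 | 0.25 | 87.5% | 87.5% | 0 | 2.5% | 2.5% |
| 0.25 | 0 | 87.5% | 84.0% | −3.5 | 0.1% | 19% |
| 0.50 | 0.25 | 91.3% | 87.5% | −3.8 | 0.1% | 25% |

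With no rescheduling in control, the full 4 points appear at *f* = 0.284 in the app arm: 0.84 / (1 − 0.0455) = 88.0%. That is 0.0455 × 235 = about 11 patients, fewer than the 262 − 235 = 27 per arm allowed for dropout.

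**What the table depends on.**

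1. *Exclusion.* Every non-zero row requires rescheduled patients to be left out. The protocol does not say so. If all randomised patients stay in and a rescheduled patient counts as not adequate, both arms return to 84.0%, provided only truly inadequate patients are rescheduled.
2. *Route.* The table sends inadequate patients to rescheduling. The Intervention section sends them to rescue. A patient who is rescued, examined as planned and found clean is a real success of the app, not a product of selection.
3. *Direction.* The app warns patients before they arrive, which leaves time for rescue. The control check happens at the hospital, and the Background calls that approach reactive. More rescheduling in control is at least as plausible as less. The algorithm's sensitivity interval in the Background, 34.2% to 100%, does not settle it.

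**The case for a change.** The strongest case for acting is that this is more than analysis detail. Whether a patient turned away for poor preparation is a failure, and which examination supplies the score, helps to define the primary outcome and affects what sites record at the index visit. The protocol names the event and places it outside the primary outcome. The checking staff are not blinded, the possible distortion is as large as the planned effect, and one paragraph would settle the matter.

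Much of this stands. The checks do differ, the rule is not written down, and the arithmetic is right under its assumptions. What does not follow is that the protocol is wrong. Listing rescheduling as a secondary outcome does not take those patients out of the primary rate. It makes a difference between the arms visible, and it means the event is already to be recorded. The protocol names a full analysis set, and an analyst would naturally keep patients rescheduled for poor preparation in it as failures.

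Nor is an explicit failure rule free of choices. Taking inadequate preparation as the positive class, the pilot specificity of 94.1% would flag 5.9% × 84% = 5.0% of the app arm although they were well prepared. If all of them were rescheduled and counted as failures, with no true benefit, app adequacy would be 84.0 − 5.0 = 79.0% against 84.0%. Staff review of the photograph makes that an upper bound. The choice is between defensible definitions, which a statistical analysis plan can make.

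**Conclusion.** No change to the protocol follows. The gap is real but is one that analysts fill sensibly: the definition of the full analysis set and the handling of patients without a score are commonly left to the statistical analysis plan, which is not at hand. No sentence in the protocol is false or contradicts another on this point.

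If rescheduled patients were left out, the distortion under no true benefit would run from +7.3 to −3.8 points over the scenarios tabulated, and would be zero with equal shares. Its sign is unknown, so a bias in favour of the app is not shown. These sizes rest on the protocol's 16% inadequate rate, on rescheduling shares that no document supplies, and on scoring at colonoscopy. The last is inferred: the primary outcome names no scale, and the Boston score appears only in the pilot results. The conclusion would change if the analysis plan restricted the primary rate to examined patients or used scores from repeat examinations.

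### The only listed harm outcome starts after colonoscopy, so no adverse-event comparison covers the earlier phase in which the app acts

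*Protocol*

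**What the plan says.** The Outcome parameters section of the protocol ends its list of secondary outcomes with "and post-procedural adverse events". No other listed outcome concerns harm. The next sentence reads: "The results will be analyzed in full analysis set, per-protocol set and safety set".

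The Intervention section places the app's steps before the examination. The first step is given as: "After taking the bowel-prep solution, patients in the app group are instructed to photograph their final stool in the toilet". Patients then send the picture to the app for rating. When the rating is unfavourable, "the app displays an alert advising the patient to come to the hospital early or contact clinical staff". On what happens next, the same section states: "clinical staffs then review the photo and decide whether a rescue preparation is needed". In the control arm the corresponding contact is verbal and concerns the stool: "before the examination, clinical staffs asked questions". The rescue product is the same in both arms; for the app arm the text says "The standard rescue was an additional packet of polyethylene glycol".

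Background and aim gives the intended mechanism: patients assess themselves and, if needed, "present early (out-patients) or alert staff (in-patients) for rescue".

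**The concern.** The arms are meant to differ before colonoscopy, in what prompts a rescue, when it is prompted and possibly how often. The alert that advises coming early is described for the app arm only. The one harm outcome is worded so that it begins once that phase is over.

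Two gaps follow from the wording. First, an adverse event between the photo or alert and the start of colonoscopy falls outside the outcome. Second, a patient whose examination is rescheduled has no post-procedural period until a later examination is done. Rescheduling is itself an outcome that the app may change, so whether a patient's harm counts depends on something that allocation may influence.

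At stake is the completeness of the safety comparison in a trial meant to confirm the tool's clinical value. The primary comparison of preparation quality is not touched.

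**Working it through.** The protocol states no figure on this point, so there is none to reproduce. The check is a count and a comparison of timing.

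**Step 1: sort the secondary outcomes (Outcome parameters).**

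| What it measures | Outcomes | Count |
|---|---|---|
| Performance or yield of the colonoscopy | caecal intubation rate, caecal intubation time, withdrawal time, PDR, ADR, aADR | 6 |
| Exposure, logistics or staff time before the procedure | rescue use, rescheduling rate, staff assessment time | 3 |
| Patient-reported, content and timing not given | satisfaction score | 1 |
| Harm | post-procedural adverse events | 1 |

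Total: 6 + 3 + 1 + 1 = 11. Concerning harm: 1. Concerning harm before the procedure: 0.

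**Step 2: set the app's steps against the harm window.**

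| Step (Intervention) | Relative to colonoscopy | Inside the listed harm outcome? |
|---|---|---|
| Photo and AI rating | before | no |
| Alert, early arrival or contact with staff | before | no |
| Staff review and decision on rescue | before | no |
| Extra packet, if given | before | no |
| Examination rescheduled | none done yet | no |
| Period after colonoscopy, including after a falsely reassuring rating | after | yes |

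**Step 3: look for text elsewhere that would widen the window.**

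- The safety set says which patients are analysed. It does not say which events count or from when.
- The χ² test in Statistical analysis applies to whatever rate is collected. It adds no outcome.
- If the adjective is loose wording for procedure-related, events from preparation and rescue are still not clearly covered.

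Nothing in the protocol extends the harm outcome to the earlier phase.

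**Step 4: size.** The protocol gives no adverse-event rate for any phase. Counts of alerts or rescues would measure exposure, not harm, so no estimate is offered.

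**The case against.** The strongest reply is that this is an omission rather than an error. An outcome list states what will be compared; it does not limit what is recorded. Event definitions and windows are often set out in the analysis plan or the case report form, and neither is shown. A safety set is named, and in practice it might be used to report every adverse event.

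Part of this stands. A reader might infer that events before colonoscopy will be lost. The protocol does not say so, and the loss would follow only if nothing beyond the listed outcome were collected. But the protocol did not leave the window open: it chose a word that restricts it. If the events are not collected, no later analysis plan can recover them.

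The second reply is that the risk looks small. The rescue product is the same in both arms, staff and not the app decide on it, and rescue use is already compared. ASA class III or IV, obstruction and active bleeding are exclusions. All of this stands and limits the importance. It does not close the gap, because the frequency and timing of rescue may still differ by arm and the early-arrival alert exists in one arm only.

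A reader might also infer that the trial has no measure of how patients experience the preparation phase. That goes too far. A user satisfaction score is listed and may bear on it, although its content is not given and it is not an adverse-event measure.

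**Conclusion.** The point holds as a matter of wording. The only harm outcome is limited to the time after the procedure, the app acts before it, and so no between-arm comparison of adverse events is specified for that phase or for patients whose examination is rescheduled. Adverse events after colonoscopy, including those that follow a falsely reassuring rating, are covered and are not at issue.

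Importance is minor to modest. The count is 0 of 11 secondary outcomes for harm before the procedure; the clinical size cannot be estimated from the document. The conclusion rests on the plain meaning of the adjective and on the absence of any wider window elsewhere in the protocol.

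Two stronger readings are not supported. The document does not show that the app causes harm: it gives no rate and describes no adverse event arising from the alert, early arrival or rescue. Nor can the missing definition of the safety set be counted as a fault, since that may properly be left to the analysis plan.

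**What to change.** Replace the last secondary outcome with: *adverse events from start of bowel preparation (or randomisation, if later) to the end of post-procedural follow-up, in all randomised patients including those whose examination is rescheduled, recorded the same way in both arms and reported separately for before and after the start of colonoscopy.*

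The words in brackets are needed because the Randomization section does not say when allocation falls relative to intake of the preparation. Reporting the two periods separately keeps the post-procedural result that the sponsor already intends. The earlier period will include some time before the photo, when the app has not yet acted, so it covers the app's phase without isolating it.

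The cost is a change of wording and slightly more data entry. There is also possible reporting bias: the Blinding section states that patients know their arm, and app patients who receive an alert may have more contact with staff. Recording events in the same way in both arms reduces this bias but does not remove it. Sample size and primary analysis are unchanged.

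### The sample size of 235 per arm does not follow from the stated 84% vs 88% adequate preparation: power is about 24%, not 80%

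*Protocol*

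**What the plan says.** The Sample Size section of the protocol starts from the control arm: "Assuming that 16 % of patients have inadequate bowel preparation with the traditional regimen". It then gives the effect and the resulting number together; the app should "convert 25 % of these failures (i.e., 4 % of the total cohort) to adequate preparation, a sample size of 235 participants is required". The error rates are alpha 0.05 "and power = 0.80". After a 10% dropout allowance it says "we plan to enroll 262 subjects per arm, for a total of 524 participants".

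The test and its sidedness are in the Statistical analysis section: rates are compared by chi-square, and "A two-sided $P < 0.05$ was considered statistically significant".

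The only effect data in the document are in the background, from the sponsor's single-centre randomised trial: "App users had significantly higher adequate-preparation rates (97 % vs 90"% (P = 0.002; 232 app and 229 control patients analysed).

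**The concern.** A 4-point difference between two rates in the mid-80s is small, and 235 per arm is far fewer than such a difference normally requires. The protocol does the conversion from 25% of failures to 4 points itself, so the target is not in doubt; the number attached to it is.

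This paragraph is the only justification for the size of the trial. If its power claim is wrong, a non-significant result on the adequacy rate would be read against 80% power that the design does not have for the stated effect. If the app did exactly what the paragraph assumes, about three trials in four would fail to show it.

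**Working it through.** **Inputs**

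- Control arm: 16% inadequate, so p1 = 0.84 adequate (Sample Size).
- App arm: 0.25 × 16% = 4 points converted, so p2 = 0.88 adequate (Sample Size).
- Alpha 0.05 and power 0.80 (Sample Size); two-sided, chi-square (Statistical analysis). Hence z = 1.960 and 0.842.
- Two equal arms, 10% dropout (Sample Size).

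**The plan's own figures.** The dropout step reproduces: 235/0.9 = 261.1, rounded up to 262, and 2 × 262 = 524. So 235 is the evaluable number per arm, although the words are missing after it. The 235 itself does not reproduce.

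**Required size.** With p̄ = (0.84 + 0.88)/2 = 0.86:

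n per arm = [1.960 √(2p̄(1 − p̄)) + 0.842 √(p1(1 − p1) + p2(1 − p2))]² / (p2 − p1)²

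- First term: 1.960 × √0.2408 = 0.9618
- Second term: 0.842 × √(0.1344 + 0.1056) = 0.4123
- n = (0.9618 + 0.4123)² / 0.0016 = 1,180.1, rounded up to 1,181 per arm

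This is 1,181/235 = 5.0 times the stated figure. With 10% dropout it becomes 1,181/0.9, rounded up to 1,313 per arm, or 2,626 in total.

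**Power at the planned size**

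Power = Φ{[0.04√n − 0.9618] / √0.2400}

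- n = 235: Φ{(0.6132 − 0.9618)/0.4899} = Φ(−0.71) = 23.8%. Exact enumeration of the chi-square test gives 24.0%.
- n = 262 (no dropout): Φ{(0.6475 − 0.9618)/0.4899} = Φ(−0.64) = 26.1%.

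The 95% confidence interval half-width for the difference at 235 per arm is 1.960 × √(0.2400/235) = 6.3 points, wider than the 4-point target.

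**Other readings of the stated inputs**

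| Reading | n per arm for 80% power |
|---|---|
| 84% vs 88%, two-sided, pooled | 1,181 |
| same, continuity-corrected | 1,230 |
| same, unpooled / arcsine | 1,178 / 1,176 |
| 84% vs 88%, one-sided, pooled | 930 |
| 16% falling *to* 4% inadequate, two-sided | 97 (113 continuity-corrected) |

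One-sample and paired formulas, which do not fit a two-arm trial, give 616 and 194 subjects (two-sided). Reading 235 as a two-arm total (117 per arm) lowers the power to 14.0%. The nearest approach is the last row of the table doubled to a total, 2 × 113 = 226. That is not 235, it contradicts the protocol's 4% of the whole cohort, and it contradicts the use of 235 per arm.

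**What 235 per arm does support.** Solving the same formula for p2 with p1 = 0.84, n = 235 and 80% power gives p2 = 0.923. That is a gain of 8.3 points, or 8.3/16 = 52% of failures converted.

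**Scenarios using the pilot's control rate**

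| Adequate, control vs app | n per arm for 80% | Power at 235 per arm |
|---|---|---|
| 90% vs 97% (pilot result) | 194 | 87.1% |
| 90% vs 92.5% (pilot control rate, stated 25% conversion) | 2,005 | 15.8% |

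**The case against.** Four points can be made for the plan.

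*The primary outcome also includes excellent preparation.* At the pilot rates for that endpoint (86.2% vs 59.8%), about 44 per arm would suffice and 235 per arm has more than 99.9% power. This stands, and it limits the consequence: the low power applies to the adequacy rate, not to everything named as primary. It does not rescue the paragraph, whose assumptions and power claim concern adequacy alone.

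*The trial may be large enough for the real effect.* At the pilot's 90% versus 97%, power at 235 is 87%. This also stands, with the caution that a single-centre pilot may overstate the effect. What is shown is a justification that does not match the number, not a trial bound to fail.

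*Some other design may lie behind 235.* A non-inferiority calculation with a 5-point margin gives 233, and 84% versus 92%, one-sided with continuity correction, gives 228. The protocol states no margin, no 8-point effect and no one-sided test, so these remain guesses. The claim is only that none of the readings of the stated inputs that were tried yields 235.

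*A separate analysis plan could settle it.* It could not. The inputs and the result stand together in the protocol, and no later document can make 84% versus 88% yield 235 at 80% power.

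**Conclusion.** The point holds and must be fixed. For the effect the protocol states, the required number is understated about fivefold and the power is about 24% against 80% claimed. This rests on the protocol's own rates, its two-sided 0.05 level and its chi-square test. The choice of variance formula, a continuity correction or one-sided testing does not change the conclusion. The statement that three trials in four would miss the benefit is conditional on a true gain of exactly 4 points in the adequacy rate.

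**What to change.** Delete the claim that 235 gives 80% power for a 4-point gain, write *per arm* after 235, and restate the justification so that effect, power and number agree. Two versions work at the planned 262 per arm:

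1. *235 evaluable patients per arm give 80% power (two-sided 0.05) to detect 84% versus 92.3% adequate preparation, that is, conversion of about 52% of failures; power for a 4-point gain is about 24%.* The second clause is essential, because the effect has been fitted to the number. The sponsor should say why a gain of this size is plausible.
2. Base the calculation on the pilot, 90% versus 97%: 194 per arm needed, 87% power at 235. This replaces the 16% control failure rate with 10%, which should be stated openly, along with the risk that one centre's result does not carry over.

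Either version costs one reworded paragraph in an amendment and no extra patients, but the detectable effect becomes less favourable than the 4 points now claimed. If a 4-point gain is truly the smallest effect the sponsor wants to detect with 80% power, rewording is not enough: about 1,181 evaluable and 1,313 enrolled per arm would be needed, 2,626 in total against the 524 planned.
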